### **Assessment of TEAEs**

The assessment whether an adverse event is a TEAE will be done after replacement of missing date/time information.

### **Assignment adverse events to time periods/trial phases**

Not applicable.

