#### **Risks related to bone biopsies**

Bone biopsies are performed as a minor outpatient surgery and are safe and generally well-tolerated (Kann et al. 2006, Hernandez et al. 2008). Risks include bleeding, hematoma, infection, superficial nerve injury, and pain. Most subjects experience soreness over the biopsy area for 4 days to 5 days. Subjects with increased risk of bleeding (e.g., hemostasis disorders, concomitant treatment with antithrombotic drugs) will be excluded from the bone biopsy assessments.

It is unknown whether a bone biopsy could trigger or worsen CRPS in patients. The limited trials in which bone biopsies were performed in patients with CRPS or similar painful conditions have not suggested that this procedure would be likely to cause severe complications or worsening of CRPS, even when performed in a CRPS-affected region. Since biopsies will be performed only in a region

free of CRPS-related signs and symptoms, this is likely to mitigate the risk of worsening of the condition.

Side effects from tetracycline are rare, but may include skin rashes, photosensitivity, nausea and diarrhea. Women of child-bearing potential using oral contraceptives will be excluded due to potential risk that tetracycline may diminish contraceptive efficacy. Subjects with known allergy to tetracyclines will also be excluded.

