### **14.1.6 Analysis of safety data**

#### **14.1.6.1 Adverse events**

A definition of adverse event is given in Section [12.3.1](#).

The original terms recorded in the CRF to identify adverse events will be coded using the most recent version of the Medical Dictionary for Regulatory Activities (MedDRA) at the time of database lock.

All adverse events occurring in a subject administered a trial treatment and which do not necessarily have a causal relationship with this treatment will be defined as TEAEs. In addition, pre-treatment adverse events which worsen during the treatment period are also considered TEAEs.

Treatment emergent adverse events will be summarized for each treatment group by System Organ Class and Preferred Term. Additional summaries by time to onset, duration, intensity, relationship to the IMP, outcome, expectedness, and countermeasures will also be created. To account for the differences in the planned trial duration of the subjects in this trial, an analysis of exposure-adjusted incidence rates will be done in addition to the analysis of crude incidence rates.

Subjects with SAEs will be summarized and additionally listed. Special attention will be given to those subjects who discontinue treatment due to an adverse event or who experience a severe or SAE.

The incidences and incidence rates of all adverse events will be summarized descriptively.

Permanent discontinuations from treatment due to adverse events will be summarized descriptively.

The distribution of time to onset of any TEAE will be summarized using time-to-event methods. A graphical display using Kaplan-Meier methods displaying subjects at risk per time point will also be produced.

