**8.2.2 Further definitions**

Term	Definition
Baseline	
For this single-arm non-randomized trial, baseline is the last observation (scheduled or unscheduled) before first IMP administration, unless specified otherwise. In general, baseline is the value recorded at Visit 2.
 
For physical examinations, a general assessment will be done at Visit 1, and at all subsequent visits (scheduled or unscheduled) the change compared to the previous visit will be assessed.
 
For bone imaging assessments, a separate baseline visit must be scheduled during the enrollment period for subjects undergoing bone densitometry and magnetic resonance imaging procedures.

Early termination visit	Subjects who discontinue the follow-up period before their last planned visit should undergo an Early Termination Visit with procedures identical to Visit 11. If a subject discontinues then, the data recorded under Visit 11 in the eCRF are treated as data belonging to the Early Termination Visit.
Follow-up period	The follow-up period starts after the treatment period and ends at Visit 11.
Follow-up completers	Subjects completing Visit 11 in the follow-up period. Intermittent missed visits in the follow-up period are allowed and do not affect the follow-up completion status.
Investigational Medicinal Products (IMP)	Neridronic acid in the form of sodium neridronate hemi hydrate 108 mg for intravenous infusion (equivalent to 100 mg neridronic acid) supplied in 8 mL of excipients. The full contents of a single ampule or vial (8 mL) will be diluted in 500 mL normal saline and administered by slow intravenous infusion (240 minutes [maximum 260 minutes]) at Visit 2, Visit 3, Visit 4 and Visit 5, resulting in a total dose of neridronic acid 400 mg.
On-treatment-period	For the purpose of this trial, the on-treatment period starts at the first IMP administration (included) and continues until the date (included) when the subject leaves the trial, i.e., at Visit 11 for trial completers, and otherwise at the Early Termination Visit for discontinued subjects. This is based on the persistence in bone and potentially prolonged effect of neridronic acid.

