### 15.1 Adverse events

All adverse events with start date/time after first IMP administration in a subject administered a trial treatment will be defined as treatment emergent adverse events (TEAE) irrespective of causal relationship.

A pre-treatment non-TEAEs is an adverse event starting in the pre-treatment period as defined in Section 8.2.2.

If there are partial dates or times, an adverse event will be considered treatment emergent unless the information available will clearly exclude it. Further details can be found in Section 20.1.6.1.

The causal relationship of TEAEs to IMP is categorized as follows:

Category	Assessment by investigator:
Related	certain probable/likely possible
Not related	unlikely not related
Unknown	unassessable/unclassifiable conditional/unclassified causal relationship is missing

A TEAE is considered to be ‘expected’ when the nature or intensity is consistent with the information in the neridronic acid investigator’s brochure. Otherwise, it is considered to be an ‘unexpected’ TEAE. Expectedness will be assessed by the sponsor.

The following overview tables will be generated overall, i.e., for the single treatment group neridronic acid 400 mg.

1. Summary of the number and percentage of subjects with at least 1:

- TEAE.
- Serious TEAE.
- Non-serious TEAE.
- Unexpected TEAE.
- Related TEAE.
- Related serious TEAEs.
- TEAE leading to discontinuation from IMP.
- TEAE leading to discontinuation from the trial.
- Deaths.

The percentage denominator will be the number of subjects.

2. Summary presenting the number of TEAEs per subject categorized as 0, 1, 2, 3, 4, 5, and >5.
3. Summary of the number and percentage of TEAEs for:
  - TEAEs.
  - Serious TEAEs.
  - Non-serious TEAEs.
  - Unexpected TEAE.
  - Related TEAEs.
  - Related serious TEAEs.
  - TEAE leading to discontinuation from IMP.
  - TEAE leading to discontinuation from the trial.

The percentage denominator will be the total number of TEAEs.

If more than 10 subjects discontinue the trial/IMP due to TEAE, the incidence and the incidence rate of TEAEs leading to discontinuation from the trial/from IMP will be summarized by SOC and PT.

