### **15.1.1 Incidence, incidence rates and number of events**

The incidence of an adverse event is defined as the number of subjects with occurrence of this adverse event during the period of interest.

The incidence rate (CIR for crude incidence rate) of an adverse event is defined as the number of subjects with occurrence of this adverse event during the period of interest divided by the total number of subjects  $n$  in the respective group (e.g., treatment group).

The incidence, incidence rate, the number of events and the percentage of events (related to the total number of events) will be summarized by PT sorted by decreasing incidence rate for:

- TEAEs.
- Serious TEAEs.
- Non-serious TEAEs.
- Related TEAEs.

A separate table per type of TEAE will be prepared. The tables will be restricted to events with an incidence rate of at least 5% ( $\geq 5\%$ ).

The incidence, incidence rate, the number of events and the percentage of events (related to the total number of events) will be summarized by SOC and PT (sorted alphabetically) for each:

- TEAEs.
- Serious TEAEs.
- Non-serious TEAEs.
- Related TEAEs.

For serious TEAEs, the incidence, the incidence rate, the number of events and the percentage of events will also be presented for serious related TEAEs, serious fatal TEAEs and serious fatal related TEAEs.

For all enrolled subjects, the incidence, incidence rate, the number of events and the percentage of events (related to the total number of events) will be summarized by SOC and PT (sorted alphabetically) for each:

- Pre-treatment non-TEAEs.
- Serious pre-treatment non-TEAEs.

Presentation will only be overall and not per treatment.

The number and percentage of events will be summarized by SOC and PT (sorted alphabetically) for the following TEAE descriptors. Presentation will be for TEAEs only.

- Intensity: mild, moderate, severe.
- Causal relationship to the IMP: related (with subcategories: possible, probable/likely, certain), not related (with subcategories: not related, unlikely), unknown (with subcategories: conditional/unclassified, unassessable/unclassifiable, causal relationship missing).
- Outcome: recovered/resolved, recovering/resolving, not recovered/not resolved, recovered/resolved with sequelae, fatal, unknown.
- Non IMP related countermeasures: none, newly started medication, trial discontinuation, others.
- Action taken with IMP: drug interrupted, drug withdrawn, not applicable, unknown.

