Denominator for percentage calculation will be the number of all TEAEs for presentation overall SOCs, and the number of TEAEs per SOC or PT respectively, for the presentation per SOC or PT, respectively.

Measures of location and variation will be calculated for:

- Duration of TEAEs.
- Time to onset of TEAE.

In addition, the time to onset of TEAE will be summarized using time-to-event methods pooled over all TEAEs. Time will be days until onset. The time to onset will be censored at the End-of-Trial-Visit, or at the time point of discontinuation if not due to TEAE.

The following listings will be produced for all enrolled subjects:

- Deaths.
- Serious adverse events other than death.

- Adverse events leading to discontinuation from the trial.
- Adverse events leading to permanent discontinuation from IMP.

In addition, adverse events associated with acute phase reaction will be presented for the SAF in a separate subject data listing. Adverse events associated with acute phase reaction include the PTs *Acute Phase Reaction* in all cases. They also include the PTs *Arthralgia*, *Bone pain*, *Chills*, *Fatigue*, *Headache*, *Influenza Like Illness*, *Musculoskeletal Chest Pain*, *Musculoskeletal Pain*, *Myalgia*, *Pain*, *Pain In Extremity* and *Pyrexia*, but only if occurring in the first 3 days after first IMP intake and not lasting longer than 3 days.

For TEAEs associated with the acute phase reaction, the incidence, incidence rate, the number of events and the percentage of events (related to the total number of events) will be summarized by PT.

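### Beyond the acute-phase table and outputs tied to infusion decisions, no TEAE table by SOC and PT separates the 10-day infusion course from the following 50 weeks

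*SAP*

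**What the plan says.** SAP Section 15.1 sets the start of the TEAE window: "All adverse events with start date/time after first IMP administration in a subject administered a trial treatment will be defined as treatment emergent adverse events", whatever the cause. SAP Section 8.2.2 sets its end: the on-treatment period "continues until the date (included) when the subject leaves the trial". The reason given is that the drug stays in bone and may act for a long time. For a completer the window ends at Visit 11, planned for Day 365.

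SAP Section 15.1.1 tabulates incidence, crude incidence rate and event counts over that window by PT and by SOC and PT. The subsection of SAP 20.1.6.1 titled "Assignment adverse events to time periods/trial phases" is marked *Not applicable*.

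SAP Section 8.2.2 nevertheless defines a treatment period (Visit 2 to Visit 5, or to the last infusion visit after permanent discontinuation of study drug) and a follow-up period (from then to Visit 11). SAP Sections 10.1 and 10.2 use both to split discontinuations from the trial.

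On timing, Protocol Section 14.1.6.1 promises more: "Additional summaries by time to onset, duration, intensity, relationship to the IMP, outcome, expectedness, and countermeasures will also be created". It also promises exposure-adjusted incidence rates alongside crude ones. SAP Section 15.1.1 gives summary statistics for time to onset, and in addition "the time to onset of TEAE will be summarized using time-to-event methods pooled over all TEAEs". It adds a table by PT for acute-phase events.

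**The concern.** The trial has one arm, and safety is its primary objective. With no comparator, the timing of an event relative to the infusions is useful evidence when a reader tries to separate reactions to dosing from a year of ordinary illness. The infusion course is a small fraction of the window, so an excess confined to it is diluted in any table that covers the whole window. The plan will report in which phase subjects left the trial, but not, term by term, in which phase their events began. The start dates needed are already collected. At stake is how interpretable the TEAE tables are, not the validity of the primary endpoint.

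**Working it through.** The plan has no figure to reproduce here. The sample size of about 290 is a safety-exposure target, not derived from an event rate or a precision goal. The check has two parts.

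**1. Does any planned output already give the split by SOC and PT?**

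- *Acute-phase table (SAP 15.1.1).* By PT. Twelve listed terms count only if they start within 3 days of the first infusion and last no more than 3 days. It is therefore not a table of reactions to infusions 2 to 4. Its list contains no ocular, renal or hypocalcemia term, although Protocol Section 8.2 discusses all three as risks.
- *Time-to-onset statistics (SAP 15.1.1).* Planned, but no breakdown by SOC or PT is specified.
- *Time-to-event summary (SAP 15.1.1).* Pooled over all TEAEs, so it shows no onset pattern for a term.
- *TEAEs leading to discontinuation of study drug, and action taken with study drug (SAP 15.1, 15.1.1).* By SOC and PT, the former only if more than 10 subjects are affected. Discontinuation of study drug applies only to the treatment period (Protocol 9.3.2), so these outputs do point to that period, but only for events that changed dosing.
- *Pre-treatment events (SAP 15.1.1).* By SOC and PT, but for all enrolled subjects and over an enrollment period of varying length, up to 60 days.
- *Exposure-adjusted rates (Protocol 14.1.6.1).* SAP 15.1.1 defines and tabulates crude rates only. SAP 20.1.6.1 gives a rule for imputed dates and zero exposure time, but no table.

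So no planned output gives the split for TEAEs in general.

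**2. How much does pooling dilute an early excess?**

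Inputs from the documents: a 10-day infusion course, Visit 6 at Week 2, a course extendable to 21 days, and a window ending at Day 365. All event rates below are assumptions, since the documents give none.

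Share of the window: 10/365 = 2.7%; 14/365 = 3.8%; 21/365 = 5.8%.

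If the event rate is multiplied by RR during the first w days only, the pooled 52-week rate is multiplied by (w × RR + 365 − w)/365.

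| RR | w = 10 | w = 14 |
|---|---|---|
| 2 | 375/365 = 1.027 | 379/365 = 1.038 |
| 5 | 405/365 = 1.110 | 421/365 = 1.153 |
| 10 | 455/365 = 1.247 | 491/365 = 1.345 |

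A single term: background 0.2 per year at a constant hazard, plus an acute effect in a fraction a of subjects.

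- 14 days, background only: 1 − exp(−0.2 × 14/365) = 0.76%.
- 14 days, with effect: 1 − (1 − a) × exp(−0.2 × 14/365) = 1.76% for a = 1% and 10.7% for a = 10%. The ratios are about 2.3 and 14.
- 52 weeks, background only: 1 − exp(−0.2) = 18.1%.
- 52 weeks, with effect: 1 − (1 − a) × exp(−0.2) = 18.9% for a = 1% and 26.3% for a = 10%. The ratios are about 1.05 and 1.45.

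In 290 subjects the 1% case is about 5 subjects against 2 in the first 14 days, and about 55 against 53 over the year.

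Any TEAE, with a 5-fold rate over 14 days:

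| Background per year | 52 weeks, without → with | 14 days, without → with |
|---|---|---|
| 0.5 | 39.3% → 43.8% | 1.9% → 9.1% |
| 1 | 63.2% → 68.4% | 3.8% → 17.5% |
| 2 | 86.5% → 90.0% | 7.4% → 31.9% |

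The pooled figure moves by 3.5 to 5.2 points and the 14-day figure by 7.2 to 24.5 points.

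**The case against.** The long window is deliberate and justified. Because the drug persists in bone, follow-up is not an unexposed period, and a late event may still be a drug effect. Adverse events are also asked about far more often early: at Days 1, 4, 7 and 10 and Week 2, then only at Weeks 6, 12, 26, 39 and 52. Some early clustering would come from questioning and shorter recall, and person-time rates do not remove that. The trial is exploratory, with no inferential testing. All of this stands. It limits what a split can show, but it does not argue for having none.

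Three stronger readings are tempting, and the documents do not support them.

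- A reader might infer that early versus late onset is the only contrast within the trial and that the plan discards it. Pre-treatment events are tabulated, laboratory values, vital signs and ECGs are compared with baseline by visit (SAP 15.2), and onset timing is partly used in the outputs listed above.
- A reader might infer that biopsy effects at Week 26 will contaminate the table of common drug events, since "Most subjects experience soreness over the biopsy area for 4 days to 5 days". But TEAEs are counted irrespective of cause, and related TEAEs have their own tables. Reaching the 5% cut needs 0.05 × 290 = 14.5, so at least 15 of about 20 biopsied subjects coded to one term. Eleven of 20, which would already be most, gives 11/290 = 3.8%.
- A reader might infer that the any-TEAE primary endpoint is bound to saturate over a year. The documents give no background rate from which to say so.

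**Conclusion.** The point holds as a gap in tabulation. TEAEs by SOC and PT are pooled from first infusion to trial exit, assignment to phases is switched off, and the existing timing outputs cover only selected terms, only events that changed dosing, or all terms together. The 52-week definition and its tables are not wrong and should stay.

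The size depends on assumptions. At a constant background of 0.2 per year and equal ascertainment over time, the 14-day contrast lost to view is about 2.3-fold for a 1% acute effect and 14-fold for a 10% effect, against about 1.05-fold and 1.45-fold in the pooled table. Neither end of that range is a prediction for this drug. This is a cheap improvement to the description of safety, not a flaw that invalidates an analysis.

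**What to change.** In SAP Section 20.1.6.1, replace *Not applicable* with a rule that assigns each TEAE, by start date, to one of two periods:

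- **Infusion period:** for example first infusion through Visit 6, or the SAP's own treatment period. Ending at Visit 6 keeps reactions in the days after the last infusion with the infusions. Visit 6 moves when dosing is extended or stopped early (Protocol 9.3.2 and 9.3.3.2), so the length varies by subject and person-time denominators are needed.
- **Follow-up:** from then to trial exit.

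In SAP Section 15.1.1, add TEAE incidence and events per person-time by SOC and PT for each period, with a row for any TEAE. This would also begin to deliver the exposure-adjusted rates promised in Protocol Section 14.1.6.1. One imputation step in SAP 20.1.6.1 sets missing start information to the first infusion, so footnote how many events fall in the infusion period through imputed dates.

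State with the tables that the split describes onset pattern and not drug versus no drug, because the drug persists in bone and questioning is denser early. A flag for events around the biopsy is optional.

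Cost: SAP wording and one additional set of descriptive tables from dates already collected. No new data and no change to the primary endpoint.

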### **List of deaths**

Death will be identified by outcome of adverse event equals “fatal”.

### **Time to onset of adverse event**

Time to onset of adverse event will be calculated based on first administration of IMP based on the imputed value for adverse event start date/time.

### **Duration of adverse event**

Duration of adverse event will be calculated based on the imputed values for adverse event start date/time and stop date/time.

If duration of adverse event could not be calculated due to unknown date information, the following assessment to categories will be used:

- If the adverse event is marked as “continuing” in the eCRF, the duration will be categorized as “continuing”

- Otherwise the duration category will be set to “missing”.

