## 8 ANALYSIS CONVENTIONS

### 8.1 General principles

If 2 or more of the population sets as defined in the SAP coincide, presentations will only be prepared for 1 population.

All presentations will be done overall, i.e., for the single treatment group neridronic acid 400 mg. The data collected and derived in the trial will be presented in subject data listings.

Data collected in this trial will be summarized according to their nature as follows:

- Continuous variables: number of non-missing observations, arithmetic mean, standard deviation, minimum and maximum values, median and quartiles. If there are less than 5 observations, descriptive statistics will be presented based on the rules specified in Section 20.1.1.2.
- Categorical variables: absolute and relative frequencies. If not defined otherwise, the percentage denominator will be the number of subjects still in the trial at the respective time point in the analyzed population.
- Time-to-event variables: number of subjects, number of subjects with event, number of censored subjects, first quartile, median, and third quartile including 95% confidence interval. For calculating the survival estimate confidence interval (CI) bounds, the log-log transformed estimate of CI bounds will be used. In addition, Kaplan-Meier estimates and plots will be provided with the respective number at risk and the Kaplan-Meier estimates at the relevant time points together with the median and its 95% CI. Censoring mechanisms will be described in the respective section.

Medical terms (e.g., prior and concomitant diseases, adverse events) will be coded via Medical Dictionary for Regulatory Activities (MedDRA), and medications will be coded according to World Health Organization Drug Dictionary (WHO-DD).

[Table 1](#) shows the use of analysis sets in different analyses as defined in Section 9.

Table 1: Use of analysis sets

	Enrolled Set	Allocated Set	SAF	FAS	TCS	PD Set
Subject disposition	X					
Discontinuations		X				
Protocol deviations			X			
Demographics			X			
Other baseline characteristics			X			
Subject medical history			X			
Previous and concomitant medication			X			
Exposure			X			
Compliance			X			
Primary safety endpoint			X			
Secondary safety endpoint			X			
Secondary efficacy endpoints				X	X	
Adverse events			X			
Laboratory values			X			
Vital signs			X			
Twelve-lead ECG			X			
Physical examination			X			
Bone turnover markers						X
Health economics data				X		

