#### **Handling of missing date information**

The term missing date/time refers to a completely missing date/time or to an incomplete date/time where parts are not available, e.g., missing hours.

If the number of adverse events with missing date information does not exceed 10% the following imputation strategy is applied.

Missing start and end date/times will be imputed conservatively, i.e., missing values will be imputed in such a way that the duration of the adverse event is considered with the longest possible duration and such that, whenever the adverse event may potentially start after first IMP administration, the adverse event will be handled as a TEAE.

I1-I4: imputation steps

C1-C4: checkpoints

Figure 2: Graphical overview about the imputation strategy

Further explanations on the flow chart:

The different steps of the displayed imputation strategy must be completed from the first to the last step. All procedures in each step must be completed in the order given.

- Imputation:

- I1: Impute with date/time of first IMP
- I2:
  - a) Impute with first calendar day and/or first calendar month.  
Imputation will be done based on the available partial information starting with month and then day. The respective first month and day will be chosen for imputation:

Missing date	Imputed date
2014-Mar	2014-Mar-01
2014	2014-Jan-01

- I2:
  - b) Impute with first hour and/or first minute.  
Imputation will be done based on the available partial information starting with hour and then minutes. The respective first hour of a day and first minute will be chosen for imputation. “00:00” will be considered as the first hour/ first minute per day.

Missing time	Imputed time
11:--	11:00
--:--	00:00

- I3: Impute with date/time of informed consent signed  
If signing of informed consent was not collected with time information set adverse event start time to 00:00.
- I4:
  - a) impute with last calendar day and/or calendar last month  
Imputation will be done based on the available partial information starting with month and then day. The respective last month and day will be chosen for imputation:

Missing date	Imputed data
2014-Mar	2014-Mar-31
2014	2014-Dec-31

For February, leap years must be taken into account when calculating the last day in February.

1.1. b: impute with last hour and/or last minute

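### As the visible SAP text reads, TEAE duration statistics cover only events with a calculable end date, so they run short when some events are long-lasting

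*SAP*

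**What the plan says.** In SAP 15.1.1, "Measures of location and variation will be calculated for" two quantities: duration of TEAEs and time to onset. SAP 8.1 lists the statistics for a numeric variable: "Continuous variables: number of non-missing observations, arithmetic mean, standard deviation, minimum and maximum values, median and quartiles".

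SAP 20.1.6.1, under the duration heading, gives the derivation: "Duration of adverse event will be calculated based on the imputed values for adverse event start date/time and stop date/time". A fallback follows: "If duration of adverse event could not be calculated due to unknown date information, the following assessment to categories will be used". Its first branch reads: "If the adverse event is marked as “continuing” in the eCRF, the duration will be categorized as “continuing". Every other such event is set to 'missing'.

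The same section, under missing date information, states the aim: "missing values will be imputed in such a way that the duration of the adverse event is considered with the longest possible duration". The scope is wide: "The term missing date/time refers to a completely missing date/time or to an incomplete date/time where parts are not available, e.g., missing hours". For end dates, the listed step I4 is to "impute with last calendar day and/or calendar last month", with a parallel rule for the last hour and minute.

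Protocol 14.1.6.1 names duration among the additional TEAE summaries.

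**The concern.** A category cannot enter a mean, SD, median or quartile. If continuing events carry only a category, whether an event counts towards duration depends on whether it ended before the subject's last contact. That selects on the quantity being described. An event that ended on a partly known date is stretched to its longest possible length, while an event that had not ended contributes no number at all.

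The trial follows subjects to Week 52, and SAP 8.2.2 runs the on-treatment period to trial exit because the drug persists in bone. Long-lasting events are therefore relevant to the safety description. SAP 15.1.1 uses time-to-event methods for time to onset, and SAP 10.2 and 15.1 use them conditionally for discontinuation. None is planned for duration, which the end of follow-up censors directly.

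**Working it through.** The plan states no duration figure, so there is nothing to reproduce. The check has three parts.

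**1. Does any rule give a continuing event a number?**
- Step I4 completes a partial end date. Of the listed steps I1 to I4, none replaces a fully absent end date with the last contact.
- Checkpoint C2 uses a completely missing end date only to decide that the event ended after first IMP.
- The duration paragraph itself presupposes that some events stay uncomputed.
- The imputation strategy applies only if events with missing date information do not exceed 10%. The SAP does not say whether continuing events count towards that limit. Either way they receive no number.

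So in the visible text the answer is no.

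**2. Direction.** Let D be the event's duration, with density f, and C the time from onset to last contact. Keeping only events with D ≤ C leaves durations with density proportional to f(d) × P(C ≥ d). Since P(C ≥ d) cannot rise with d, the retained durations are stochastically shorter than the true ones, provided D and C are independent.

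Small example: durations 2, 3, 5 and 10 days, plus one event continuing at 300 days.
- Events with an end date: mean (2+3+5+10)/4 = 5.0; median (3+5)/2 = 4; n = 4.
- All five: mean above (20+300)/5 = 64; median 5.
- Kaplan-Meier with the fifth event censored: survival 0.8, 0.6, 0.4 and 0.2 after days 2, 3, 5 and 10, so the median is 5.

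**3. Illustrative size (all distributions assumed).** Cut-off at Day 365 (the planned Visit 11 day in SAP 20.1.1.14) and 1,000,000 simulated events per scenario (Kaplan-Meier on 100,000). A share of events is long-lasting (exponential, mean 180 or 365 days) and the rest short (exponential, mean 5 days). Days, except where shown:

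| Onset | Long share, long mean | Continuing | True mean | Mean, end date only | True median | Median, end date only | Kaplan-Meier median |
|---|---|---|---|---|---|---|---|
| first 14 days | 5%, 180 | 0.7% | 13.8 | 10.2 | 3.73 | 3.69 | 3.71 |
| uniform | 20%, 180 | 9.7% | 40.2 | 15.3 | 4.82 | 4.12 | 4.84 |
| first 14 days | 20%, 365 | 7.5% | 77.0 | 24.6 | 4.85 | 4.27 | 4.84 |
| uniform | 30%, 365 | 20.0% | 113.6 | 18.4 | 6.13 | 4.21 | 6.14 |

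The first and last rows are the extremes of 16 scenarios:
- Mean: lower by (13.8−10.2)/13.8 = 26% to (113.6−18.4)/113.6 = 84%.
- Median: lower by (3.73−3.69)/3.73 = 1% to (6.13−4.21)/6.13 = 31%.
- Kaplan-Meier median: within 0.04 days of the true median in all 16.

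A second set used a single exponential distribution, follow-up of 364 days, and onset either uniform or half in the first 14 days. True means of 90, 180 and 365 days were reported as 63.1 to 74.5, 86.7 to 108.3 and 102.3 to 132.4. A true mean of 5 days was reported as 4.9 to 5.0.

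**The case against.** A reader might infer that unresolved events vanish from the report. The documents do not support that. The duration rule gives them their own category, distinct from 'missing'. SAP 15.1.1 tabulates every TEAE by outcome, including not recovered and recovering, by SOC and PT, and all data are listed. What is lost is their contribution to the numeric duration statistics. The outcome table shows how many events are unresolved but does not correct those statistics.

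A reader might also infer that the SAP expressly excludes continuing events. It does not say so in words, and the flow chart in Figure 2 is not available. The exclusion follows because a category has no numeric value and no listed step supplies one.

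A third tempting reading is that duration will be understated several-fold. That rests on assumed mixes. Protocol 6.3 describes drug-related events as mainly fever and flu-like symptoms, and Protocol 8.2 says such symptoms usually settle within 24 to 48 hours. With nearly all events that short, the bias is negligible. Protocol 12.3.1 also has events followed to resolution or stability, so some events open at the last visit might gain an end date, although documentation stops at the last scheduled contact. Stretching partial end dates pulls the other way, so the net direction in real data depends on the mix.

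Finally, the large differences concern the mean, whereas the Kaplan-Meier remedy reports the median and quartiles. That is fair. In a mostly short mix the median gains little; the practical gain is an honest label and a visible count of continuing events.

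**Conclusion.** The point holds as a limited one. On the visible text, continuing TEAEs receive neither a numeric nor a censored duration, so the statistics in SAP 15.1.1 describe events with a calculable end date. Leaving out continuing events biases these statistics short whenever long-lasting events occur, contrary to the longest-duration aim of the same section. Among the assumed mixes tried, with 0.7% to 20.0% of events continuing, the mean fell by 26% to 84% and the median by 1% to 31%. These are illustrations that assume duration is independent of follow-up time. They do not predict this trial's results.

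The consequence is small. The summary is descriptive, in a single-arm trial with no inferential testing. The primary endpoint (occurrence of any TEAE) and the secondary endpoints are unaffected. This is a desirable improvement, not a flaw that threatens the trial's conclusions.

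**What to change.** In SAP 15.1.1 and 20.1.6.1, add a Kaplan-Meier summary of TEAE duration: median and quartiles under the general time-to-event conventions of SAP 8.1, with continuing events censored at the subject's last contact. SAP 8.1 leaves censoring rules to the individual sections, so state the rule there. Report the number and percentage of TEAEs continuing beside it. If the plain mean, SD, median and quartiles are kept, label them 'events with an end date only'.

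The cost is a short SAP edit and one extra output; no new data are needed. Reported durations will be longer, and a quartile may not be reached. Confidence intervals need care, because a subject can contribute several events and the standard intervals treat them as independent. Censoring at last contact also assumes that dropout is unrelated to how long an event lasts.
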